## APPLICATION TO USE HUMAN RESEARCH SUBJECTS

---

9. This project will be conducted at the following location(s): (please indicate city & state)
- Purdue West Lafayette Campus
- Purdue Regional Campus (Specify): \_\_\_\_\_
- Other (Specify): Indiana Nutrition Education Program class locations throughout Indiana, these may include: Emergency food distribution centers; Supplemental Nutrition Assistance Program (SNAP) offices; Women, Infant, and Children Program (WIC) offices; participant homes
10. If this project will involve potentially vulnerable subject populations, please check all that apply.
- Minors under age 18
- Pregnant Women
- Fetus/fetal tissue
- [Prisoners Or Incarcerated Individuals](#)
- University Students (PSYC Dept. subject pool \_\_\_\_)
- Elderly Persons
- Economically/Educationally Disadvantaged Persons
- Mentally/Emotionally/Developmentally Disabled Persons
- Minority Groups and/or Non-English Speakers
- Intervention(s) that include medical or psychological treatment
11. Indicate the anticipated maximum number of subjects to be enrolled in this protocol as justified by the hypothesis and study procedures: 800 (400 for control group and 400 for experimental group)
12. This project involves the use of an **Investigational New Drug (IND)** or an **Approved Drug For An Unapproved Use**.
- YES       NO
- Drug name, IND number and company: \_\_\_\_\_
13. This project involves the use of an **Investigational Medical Device** or an **Approved Medical Device For An Unapproved Use**.
- YES       NO
- Device name, IDE number and company: \_\_\_\_\_
14. The project involves the use of [Radiation or Radioisotopes](#):
- YES       NO
15. Does this project call for: (check-mark all that apply to this study)
- Use of Voice, Video, Digital, or Image Recordings?
- Subject Compensation? Please indicate the maximum payment amount to subjects. \$100  
[Purdue's Human Subjects Payment Policy](#)      [Participant Payment Disclosure Form](#)
- VO2 Max Exercise?
- More Than Minimal Risk?
- Waiver of Informed Consent?
- Extra Costs To Subjects?
- The Use of Blood?      Total Amount of Blood \_\_\_\_\_  
Over Time Period (days) \_\_\_\_\_
- The Use of [rDNA or Biohazardous materials](#)?
- The Use of Human Tissue or Cell Lines?
- The Use of Other Fluids that Could Mask the Presence of Blood (Including Urine and Feces)?
- The Use of Protected Health Information (Obtained from Healthcare Practitioners or Institutions)?
- The Use of academic records?
16. Does investigator or key personnel have a potential financial or other [conflict of interest](#) in this study?

YES       NO

## APPLICATION NARRATIVE

### A. PROPOSED RESEARCH RATIONALE

The Supplemental Nutrition Assistance Program-Education (SNAP-Ed) is an educational program offered to SNAP participants. The Nutrition Education Program (NEP) through Purdue University Health and Human Sciences Extension administers SNAP-Ed in Indiana. The NEP curriculum comprises 10 lessons that are focused on nutrition and food resource management.

The goal of this study is to determine the efficacy of SNAP-Ed to improve the immediate and long-term dietary quality (using the Healthy Eating Index (HEI)), BMI (measured height and weight), and food security (using the 18-item US HFSSM) and how the provision of SNAP-Ed with the presence of other characteristics can mediate improvement in these outcomes. Previous studies by [name] have shown significant improvements in household food security over short-term periods and a 1-year longitudinal period among Indiana NEP participants; however, the impact of SNAP-Ed on participants' dietary quality and BMI remains to be investigated. The hypothesis of this study is that dietary quality and food security will improve and BMI will remain steady over the short-term, and these improvements will be maintained over a 1-year, or "long-term", time frame in participants receiving SNAP-Ed compared to those not receiving SNAP-Ed. Results may be used as a basis for changes to the program or policies relevant to SNAP-Ed and other nutrition education programs throughout the US.

### B. SPECIFIC PROCEDURES TO BE FOLLOWED

NEP educators are considered key personnel because they will have direct contact with study participants; however, they will not have any part in data entry, analysis, or dissemination of study results. NEP educators, employees of Purdue University Extension, across Indiana will help facilitate the study. NEP educators have completed CITI training as a requirement for employment through Purdue University Extension. Before recruiting study participants, participating NEP educators will attend training sessions facilitated by the co-investigators of the study. The training sessions will include instructions on how to interact with participants; answer questions related to the study; and protocol for administering surveys, measuring height and weight, keeping participant information private, and the use of identification numbers. The study goals and hypothesis will not be shared with the NEP educators in order to keep their work with the participants as unbiased as possible.

NEP educators will recruit study participants who are interested in participating in NEP. The details of recruitment are described in Section D. A screening survey determining eligibility will be administered in addition to an explanation of consent. After completion of the screening survey and consent process, NEP educators will randomize participants into one of two groups: control or experimental. The NEP educators will be assigned a random number using Excel and then listed in order from least to greatest according to their random number. The first half of the NEP educators will assign their first recruited participants to the experimental group. After the first assignment, they will alternate assigning participants to either study group in an "every other" participant fashion. The second half of the NEP educators will assign their first recruited participants to the control group. After the first assignment, they will also alternate assigning participants to either study group in an "every other" participant fashion. The control group will wait 1 year from taking the second survey before starting NEP lessons. The experimental group will start NEP lessons immediately. Participants in the experimental group must take at least the first 4 NEP lessons within a time period of 4 to 10 weeks. The NEP SNAP-Ed curriculum includes 10 lessons, and participants may take the additional 6 lessons if desired.

All participants will complete three 30 minute surveys throughout the study. Surveys will be administered by NEP educators using the Qualtrics Offline Application on their program-provided iPads or paper surveys. The first survey will be administered upon enrollment in the study. Participants in the experimental group will take the second survey after they have completed the first 4 lessons between 4 and 10 weeks after enrollment in the study. Control participants will take the second survey after 4 to 10 weeks with no lessons. Since participants will be recruited on a rolling basis, they will take surveys at different times within a designated time

period. The third survey will be administered to both groups 1 year after the second survey. Surveys are comprised of the US Household Food Security Survey Module from the United States Department of Agriculture Economic Research Service, questions querying household and individual level characteristics, and the Indiana Food and Nutrition Program Evaluation Tool.

Participants will also complete two 24-hour dietary recalls using the Automated Self-Assisted 24-hour recall (ASA-24) and one food frequency questionnaire (FFQ) using the Diet History Questionnaire II (DHQ II) at each data collection time point. Both instruments are online and complementary dietary assessment tools created by the National Cancer Institute and have a respondent and researcher website. Results will be analyzed by the researchers using the researcher website. One dietary recall and the FFQ may be administered by the NEP Educators immediately following the in person survey, or a link to complete the dietary recall and FFQ online will be emailed to the participant within 2 days, or the participant can request to complete the dietary recalls and FFQ over the phone with the co-investigators at Purdue within 7 days after completing the survey. A script will be provided for the Purdue researchers to administer the dietary recalls and FFQ. The completion of the dietary recalls and the FFQ is necessary to perform complex modeling techniques for estimating *usual* dietary intake. The program that administers the dietary recalls assists participants through the recall process using an animated guide with audio and visual cues. Previous research has shown that the majority of Indiana SNAP-Education participants have a computer with high-speed Internet connection in their home or residence. Participants without email, without access to a computer with internet, or with limited computer skills will be instructed to complete the assessments via telephone with assistance from researchers. If assistance from researchers is needed via telephone, participant identifying information will not be collected at that time. Participants will be identified only by their participant identification number, which they will receive upon enrollment in the study. Participants will provide days and time frames over the following week when they will be available to complete the dietary assessments over the phone with Purdue researchers. In addition, participants may call the co-investigator's Purdue office phone number any time after the survey for assistance with completing the dietary assessments. If the first dietary recall and FFQ have not been completed within 4 days after the survey, researchers will call the participant no more than once per day to complete the first dietary recall and FFQ over the phone at that time or to set up appointments to complete the dietary recalls and FFQ over the phone with researchers within the 7 days after completing the in person survey. The second dietary recall should be completed 24 hours after the first dietary recall at the earliest but before 9 days after completing the in person survey. Participants will have the same options as described above to complete the second dietary recall.

In addition to the survey, dietary recalls, and FFQ, NEP educators will take height and weight measurements on each participant at each assessment time point. Weights will be measured using the SECA 869 mobile medical flat scale with remote display. Heights will be measured using the SECA 213 mobile stadiometer. This weight scale and stadiometer are research grade measurement tools. Height and weight measurements will be taken following the Centers for Disease Control and Prevention (CDC) National Health and Nutrition Examination Survey (NHANES) anthropometry manual guidelines. Height and weight measurements will be completed in a private setting or privacy screens will be used. Only the NEP educators will be able to see the measurements. Three measurements will be taken at each assessment time point in order to calculate an average. Participants will be allowed to know their measurements upon request at the time of measurement. Researchers will use these measurements to calculate BMI.

An in person survey, two dietary recalls, one FFQ, and height and weight measurements will be completed for each participant at each of the three assessment time points. The first and third assessments will cover a reference period the past 12 months, while the second assessment will cover the past 30 days. Participants randomized to the control group will be provided the opportunity to complete the SNAP-Education program at the completion of the study.

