### **C. SUBJECTS TO BE INCLUDED**

**Describe:** The inclusion criteria for the study population includes: an interest in taking NEP lessons, willingness to wait 1 year to start NEP lessons, eligibility for SNAP, age of at least 18 years, not pregnant, living in a household located in Indiana, ability speak and read English, willingness to complete three 30 minute surveys at the designated time intervals, willingness to provide height and weight measurements, willingness to complete one 30 minute dietary recall and 60 minute FFQ at each assessment time point, willingness to stay in touch with NEP educators, and no previous participation in NEP lessons within the last year.

The exclusion criteria only include not meeting the inclusion criteria.

Women who are pregnant will not be able to enroll in the study; however, once recruited, participants who become pregnant during the study period will be able to continue participating in the study.

The study population may be considered vulnerable because they are a low income and low resource population that may have a lower than average level of education. Precautions will be taken to minimize potential risks to the study population.

The maximum number of participants targeted for the study is  $n=800$ ,  $n=400$  in the control group and  $n=400$  in the experimental group. Previous studies were used to calculate these estimates. Based on these “short term” studies, a 7% rate of attrition ( $n=17$  out of 236) is expected to increase to approximately 40% ( $n\approx 320$  of 800) in the proposed study due to the duration of 1 year between the post-assessment and the follow-up assessment. Based on these attrition considerations and our previous work, a sample size of  $n=800$  will be the recruitment goal (control group  $n=400$  and intervention group  $n=400$ ) with an approximate final sample size of  $n=480$  expected.

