**D. RECRUITMENT OF SUBJECTS AND OBTAINING INFORMED CONSENT**

NEP educators will recruit potential clients for the study. NEP educators will administer a screening survey to determine eligibility for the study. If potential participants do not wish to participate in the study or complete the screening survey, they may proceed with taking NEP lessons as usual without any effect on their relationship with the NEP, NEP educator, Extension, state or federal programs, or Purdue University. Study participants and non-participants may receive NEP lessons together without any effect on the study.

If a NEP client is eligible and willing to participate in the study, an informed consent form requiring their name and signature will be provided unless the IRB approves a waiver of signed consent, in which case NEP educators will explain the informed consent form to participants and allow them to read the consent form. If the consent form is provided electronically online, participants will be asked to select the “I agree” radio button to provide informed consent before proceeding to complete the survey. Participants will be provided their choice of an email or physical copy of the informed consent form.

NEP educators will facilitate data collection and use identification numbers to keep participant data together. NEP educators also collect private identifying information such as names, home addresses, email addresses, and telephone numbers for the NEP, but not as part of the study. The study investigators and co-investigators will receive the data with the participant identification numbers only and without any private identifying information. Researchers will be provided with only participant phone numbers and email addresses which will be linked only to participant identification numbers and never linked with participant names.

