## **K. WAIVER OF INFORMED CONSENT OR SIGNED CONSENT**

Researchers are requesting a waiver of signed consent for individuals who prefer to complete all tasks including consent electronically; however, the individual will be present to complete the verbal consent process whether he/she signs the form or provides consent electronically. Participants will be provided the attached informed consent form after the being screened for study eligibility and before proceeding to complete the in-person survey. If participants complete the screening survey electronically through the Qualtrics application on the NEP educator's iPad, they will be required to provide informed consent by selecting the "I agree" radio button at the bottom of the informed consent form before proceeding to complete the survey. If participants complete the screening survey in paper form, then they will be provided an informed consent form that will not require a signature. All participants will be provided a copy of the informed consent form through their choice of email or a paper copy.

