## SNAP-Ed Sequel Statistical Analysis Plan

**Methods:** Up to 2 repeated online 24 hour dietary recalls using the Automated Self-Assisted 24-hour Recall (ASA-24) and the Diet History Questionnaire II (DHQ II) (web-based food frequency questionnaire) developed and provided by the National Cancer Institute will be used to estimate dietary intake; the Estimated Average Requirements (EAR) for nutrients (or Adequate Intake(AI) for nutrients that do not have an EAR) will be used as a dietary reference; the Healthy Eating Index-2010 will be used to characterize diet quality using data collected from the ASA-24; the 18-item US Household Food Security Survey Module (USHFSSM) will be used to assess household food security; the Nutrition Education Program (NEP) Medium Term Survey and additional questions will be used to assess participant characteristics, nutrition and health knowledge, and nutrition and health behavior

**Characteristics:** Study participant characteristics at baseline will be compared across the intervention and control groups to test for potential confounders to test for in regression models. Characteristics of participants who withdrew from the study will also be compared to those who completed the study.

**Diet Quality:** The Healthy Eating Index-2010 scoring algorithm will be used to characterize diet quality. Instructions and sample SAS code are provided by the National Cancer Institute website at <https://epi.grants.cancer.gov/hei/>. The simple algorithm will be used in order to assign HEI scores to each individual to be able to match and compare individual participants over time using regression modeling. Change in diet quality in the intervention group compared to the control group over time is one primary outcome.

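### Assignment depends only on screening and consent, and nothing holds assignment or disclosure of the arm until baseline data are collected

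*Protocol*

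**What the plan says.** Protocol Section B sets the earliest point of assignment: "After completion of the screening survey and consent process, NEP educators will randomize participants into one of two groups: control or experimental". The step before it is also described there: "A screening survey determining eligibility will be administered in addition to an explanation of consent". Later in the same section: "The first survey will be administered upon enrollment in the study". Section B does not say whether enrollment means consent or assignment.

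Section K gives participants the consent form "after the being screened for study eligibility and before proceeding to complete the in-person survey". Section D has those who consent online "select the “I agree” radio button to provide informed consent before proceeding to complete the survey". Neither section mentions assignment, and no section says when participants learn their arm.

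For baseline diet, Section B offers three routes for the first recall and the FFQ: with the educator straight after the survey, through an emailed link, or by telephone within 7 days of the survey. The second recall comes at least 24 hours after the first and before day 9 after the survey. Lessons in the experimental arm begin at once.

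The SAP names three primary outcomes, all dietary: change in diet quality between arms, change in usual nutrient intake from baseline to 1 year between arms, and the proportions at risk or at low risk of inadequacy. Change in food security from baseline to 1 year is to be analysed with a mixed model. The SAP also states: "Study participant characteristics at baseline will be compared across the intervention and control groups to test for potential confounders".

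**The concern.** An educator who follows Section B literally may assign as soon as consent is given. The participant then answers the food security module and behaviour questions, put by the educator who made the assignment, knowing either that lessons start now or that they are more than a year away. For controls the wait is 1 year from the second survey, which itself falls 4 to 10 weeks after enrollment. That is about 52 + 4 = 56 to 52 + 10 = 62 weeks.

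Two things are at stake.

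- **Biased baseline.** Answers given with knowledge of the arm can shift one arm's baseline mean, and between-arm comparisons of change carry that shift into the estimated effect. The SAP's comparison of baseline characteristics could then treat a consequence of assignment as a potential confounder.
- **Loss before any baseline.** A person who leaves between assignment and the first survey has been assigned but has no baseline or outcome value. This loss can differ by arm, and later modelling has little to recover it with.

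**Working it through.** **1. The plan's own figures.** Protocol Section C expects 40% attrition from 800: 800 × (1 − 0.40) = 480, and 480 / (1 − 0.40) = 800. The earlier attrition rate is 17/236 = 7.2%, stated as 7%. These reproduce, and the order of procedures changes none of them. The documents give no effect size, SD or power, so the bias cannot be set against a planned effect.

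**2. What each section fixes about the order.**

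| Protocol section | Fixed | Left open |
|---|---|---|
| B, assignment | after screening and consent | before or after the first survey |
| B, first survey | at enrollment | whether assignment has happened |
| D and K | consent before the survey | where assignment falls |
| B, dietary instruments | days counted from the survey | any link to assignment or disclosure |

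Two sequences satisfy all four rows:

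- (i) screen, consent, assign, survey;
- (ii) screen, consent, survey, assign.

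Under (i), every baseline measure follows assignment. Under (ii), with assignment at the enrollment visit, the second recall still follows it, being at least 24 hours after the first. So do the first recall and FFQ whenever they are done by link or telephone on a later day.

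**3. Dietary window against lesson start.** Assume lesson 1 on day 0 and four lessons evenly spread over the permitted 4 to 10 weeks, and count lessons up to day 8, the last day before the window closes.

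- Interval = weeks × 7 / 4: 7 days at 4 weeks gives lessons on days 0 and 7, so 2 lessons. At 10 weeks the interval is 17.5 days, so 1 lesson.
- Interval = weeks × 7 / 3 (last lesson at the end of the period): 9.3 or 23.3 days, so 1 lesson in either case.

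On these assumptions, 1 to 2 lessons can precede a baseline recall.

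**4. Effect of a shifted baseline.** Let knowledge of the arm (or an early lesson) move the experimental arm's baseline mean by b, with follow-up unaffected. Let ρ be the slope of follow-up on baseline.

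- Change contrast: (F_E − (B_E + b)) − (F_C − B_C) = true contrast − b.
- Baseline-adjusted contrast: true contrast − ρb.

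| b (points) | change score | adjusted, ρ = 0.3 | adjusted, ρ = 0.5 | adjusted, ρ = 0.7 |
|---|---|---|---|---|
| 1 | −1 | −0.3 | −0.5 | −0.7 |
| 2 | −2 | −0.6 | −1.0 | −1.4 |
| 3 | −3 | −0.9 | −1.5 | −2.1 |

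Both b and ρ are assumptions. The SAP does not say whether its regression models adjust for the baseline value.

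**5. Loss before the first survey.** If 2% to 5% of the 400 controls left at this point (assumed), 0.02 × 400 = 8 to 0.05 × 400 = 20 people would have no baseline or outcome data.

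**The case against.** The strongest reply is that the wording on assignment sets an earliest point and nothing more. Sections D and K run from consent on to the survey, so consent, survey, then assignment complies fully. This stands: a reader might infer that the plan states assignment before the first survey, and it does not. The gap remains, because nothing requires the protective order and educators at sites across Indiana could each apply a different one.

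Other stronger readings also fail.

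- **That eligibility closes too early.** Every inclusion criterion in Section C is settled at screening or is a statement of willingness, and "The exclusion criteria only include not meeting the inclusion criteria". No survey answer or measured height, weight or BMI can make an assigned person ineligible.
- **That reordering would keep the educator unaware of the arm.** Strict alternation lets the educator foresee the next assignment before meeting the participant. That is a separate concealment problem, and reordering protects only the participant's answers.
- **That every outcome is exposed.** Height and weight are averages of three readings on research-grade equipment, which leaves little room for a shift, and the SAP does not specify an analysis of BMI.
- **That early leavers cannot be described at all.** They may have screening data.

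There are partial safeguards. Participants must accept a 1-year wait before they can be assigned, and educators are not told the goals or hypothesis. The 8 to 20 people above are also few beside the 320 losses already expected. These points limit the likely size, but they do not stop participants from reporting baseline diet or food security with knowledge of their arm.

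It is also fair to say that securing only the survey and the measurements would miss the primary outcomes, which come from the dietary instruments. The fix has to cover those as well.

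**Conclusion.** The point holds as a gap in sequencing. Assignment is tied only to screening and consent, and no baseline measure has to be complete before the arm is assigned or disclosed. Assignment ahead of the survey and measurements is the natural reading but is not stated. Exposure is clearest for the dietary instruments, which can fall after assignment, and possibly after a lesson, under either order.

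The size is unknown. The illustrative bias is 1 to 3 points on a change score, or 0.3 to 2.1 points with baseline adjustment. It assumes that the shift occurs in one arm and affects baseline only; a reporting shift that persisted equally to follow-up would cancel in a change score. The figure of 8 to 20 early losses rests on an assumed 2% to 5%. The change is still worth making, because it is cheap and the bias could not be removed with confidence after the data are in.

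**What to change.** 1. In Protocol Section B, write the order out: screening; consent; in-person survey with height and weight; first recall and FFQ where the existing same-visit option is used; only then assignment and disclosure to the participant. Make completion of the in-person baseline a condition of assignment.
2. Record the dates of assignment, disclosure, first lesson and each baseline dietary instrument.
3. Add to the SAP a sensitivity analysis limited to dietary baseline data collected before disclosure. Where assignment follows at the same visit, this leaves at most one recall per person. It can then support diet quality scores and mean intakes, but cannot by itself separate within-person from between-person variation.
4. The investigators should reconcile the immediate start of lessons with the baseline dietary window, both in Section B.
5. Deal with the educator's ability to foresee the arm separately, under allocation concealment.

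The cost is protocol wording, a line in educator training, a few date fields and one extra analysis. A few people will complete a baseline survey paid at $5 and then not be assigned, and some visits will run longer. No additional visit is needed.

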**Raffle:**

- Participants who complete the final survey before January 1st, 2017 will be entered into a \$500 raffle. The odds of winning are approximately 1 in 480 and one \$500 check will be awarded. The odds of winning may be updated on the study reminder flyer to reflect actual number of participants. The winner

will be randomly chosen by April 1st, 2017. If researchers are unable to contact the winning participant through their NEP Assistant after 3 attempts within one week (phone call, mailing, email), another participant will be randomly chosen. The winning participant may decline the \$500. The winning participant's name, address, and social security number or taxpayer identification number will need to be shared with researchers at Purdue only if they win the raffle and only for dispersing the \$500 check. The participant will also need to complete the Institutional Review Board Human Subject Receipt Log, which will be provided by the researchers. Non-resident alien recipients will have to complete information within the Glacier Tax Compliance software system ([www.online-tax.net](http://www.online-tax.net)) to assess tax reporting and withholding requirements. This is explained in the consent form. Other than previously stated, no payment or additional action is required to enter the raffle. Participation in additional research or other consideration is not necessary. Void where prohibited or restricted by law. Subject to all federal, state, and local laws.

- The raffle will be advertised on the scheduled email and physically mailed flyers and through phone calls to participants.

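### Allocation is called randomisation, but only each educator's starting arm is random; later participants alternate, so the recruiting educator knows the next arm, and no concealment is described

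*Protocol*

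**What the plan says.** Protocol section B states that "NEP educators will randomize participants into one of two groups: control or experimental", after screening and consent. The mechanism follows. Each educator receives a random number in Excel, and the educators are ranked by it and split in half. "The first half of the NEP educators will assign their first recruited participants to the experimental group"; the other half start with control. For both halves the rule from there is the same: "After the first assignment, they will alternate assigning participants to either study group". Later in section B, control participants are again described as randomised.

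Under sections B and D the same educators recruit clients, administer the screening survey, take part in consent and make the assignment. A client who does not join the study may still take lessons in the usual way (section D).

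Three provisions bear on selection:
- Section B: "The study goals and hypothesis will not be shared with the NEP educators".
- Section C makes "willingness to wait 1 year to start NEP lessons" an eligibility item for everyone.
- The SAP (Characteristics) compares baseline characteristics between arms to find potential confounders for the regression models.

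Neither document mentions a concealed list, envelopes, central release or any other way of hiding the next assignment. No baseline measurement is required before assignment.

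**The concern.** Random allocation protects a comparison only if the person enrolling participants cannot foresee the next arm. Here that person can. An educator who knows that the next client will wait a year, or will start lessons now, can decide whom to approach, when, and in what order. Recruitment is rolling and clients outside the study can take lessons anyway, so holding someone back costs the client nothing. Assigning after consent does not help, because the arm is already known before the client is approached.

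The diet-quality and nutrient-intake outcomes in the SAP are largely changes over time. A stable baseline gap between arms largely cancels in a change. A gap in how much participants were going to change anyway does not cancel, and would be read as an effect of SNAP-Ed. Section A says the results may be used to change programs or policy, so the strength of evidence that the word randomise implies matters.

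**Working it through.** **Plan's own figure.** Section C expects 40% attrition from 800: 800 × (1 − 0.40) = 480 completers, as stated. Alternation keeps each educator's arms within one participant of each other, so the 400/400 target is not affected. The issue is selection, not sample size.

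**Predictable share.** One draw per educator fixes that educator's whole sequence. If the starting arm is not known in advance, assignments 2 to m are still certain, so the share is (m − 1)/m. The documents do not give the number of educators, so m is an assumption:

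| Assumed m | Known in advance |
|---|---|
| 4 | 3/4 = 75% |
| 10 | 9/10 = 90% |
| 20 | 19/20 = 95% |
| 40 | 39/40 = 97.5% |

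**Comparison with blocked lists, by simulation.**
- Fixed blocks of 4, with the size known to the educator: about 27% to 34% of assignments are certain over the same range of m.
- Blocks of 4, 6 and 8 mixed at random, against a guesser who knows the possible sizes and makes the best guess each time: about 2.4% are certain for lists of 14 and of 40. Correct guesses are 66.7% and 67.6%, where chance is 50%. The alternation figures for those lengths are 13/14 = 92.9% and 39/40 = 97.5% certain.

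Mixed blocks remove nearly all certainty but not all predictability.

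**How large a selection gap would matter.** This is a scale, not an estimate. With 240 completers per arm (480 in equal arms), the standard error of a difference in mean change is √(2/240) = 0.0913 SD of change. The error rate of a nominal 5% two-sided test when there is no intervention effect is P(|Z| > 1.96), with Z centred at gap/0.0913:

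| Gap in expected change | Error rate |
|---|---|
| 0.02 SD | 5.6% |
| 0.060 SD | 10% |
| 0.102 SD | 20% |

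Nothing in the documents says whether any such gap exists.

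**Is enrolment still open?** The raffle in section C is for "Participants who complete the final survey before January 1" of 2017. Section B says "The third survey will be administered to both groups 1 year after the second survey", which puts the second survey at or before 31 December 2015. It also says "Control participants will take the second survey after 4 to 10 weeks with no lessons", and intervention participants have the same window. Counting back 4 weeks gives enrolment by 3 December 2015; 10 weeks gives 22 October 2015. The raffle odds of about 1 in 480 match the whole expected final sample. Closed enrolment is therefore likely, but the document's current date is not shown, so it remains an inference.

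**The case against.** The strongest reply is that section B hides nothing. It sets out the full rule straight after the word randomise, and the rule has a real random element: educators are ranked at random, so before the draw each participant has about a one-half chance of either arm. That stands. A reader might infer that the trial is not randomised in any sense, but that ignores the random starting arm. The accurate label is alternation with a randomly assigned start.

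The safeguards also count. Withholding the hypothesis weakens the motive to select. Requiring everyone to be willing to wait limits differential refusal. The SAP's baseline comparison allows adjustment for what was measured. None of these hides the next arm, and the last cannot reach unmeasured differences in expected change.

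Three further inferences are tempting and are not supported:
- **That all assignments are known in advance, including each educator's first.** The protocol does not say when educators learn their starting arm.
- **That a particular trait, such as readiness to change, goes unmeasured.** The SAP says the surveys cover nutrition and health knowledge and behaviour, and the instruments themselves are not in the documents reviewed.
- **That this point dictates educator random effects in the main model.** Clustering by educator concerns variance, not foreknowledge. Any prescription would rest on an educator count and intraclass correlations that the documents do not give.

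**Conclusion.** The point holds as a fault in the text: the allocation is labelled as randomisation of participants, it operates as alternation after a random start, and concealment is absent. None of this depends on an assumed number. The predictable share does: 75% to 97.5% for an assumed 4 to 40 participants per educator.

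What does not follow is that selection took place or that the arms differ. The documents give no basis for the size or direction of any bias, and the error rates above show only how large a gap would have to be. The conclusion is that section B, followed exactly, leaves allocation open to selection that the SAP's baseline comparison cannot fully repair, and that a report relying on its wording would overstate the strength of the design.

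**What to change.** **If enrolment is open.** Replace alternation in section B with a list generated by the research team, stratified by educator, with block sizes mixed at random (for example 4, 6 and 8) and not disclosed to educators. Reveal each assignment singly, for example in sealed, opaque, numbered envelopes, only after eligibility, consent, the in-person baseline survey, and height and weight are recorded. The cost is an amendment, a list and envelopes for each educator, and brief training. Arm sizes within an educator could differ by up to 4 (half of an unfinished block of 8), against 1 under alternation. No extra participants are needed.

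**If enrolment is closed.** Describe allocation in the protocol, SAP and report as alternation with a randomly assigned starting arm per educator (quasi-randomised), and stop using randomise without that qualification. Report baseline characteristics by arm, within educator if an educator code is available, and report departures from strict alternation. Limit causal wording accordingly. The cost is wording and one table. The documents do not say that an educator code is recorded in the analysis data, and section F leaves the participant code key with the educators, so availability must be checked.

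**Optional in either case.** A test of educator-level differences between arms can serve as a sensitivity analysis. It needs the educator code, and educators with completers in only one arm drop out of it. It addresses clustering and does not repair selection.
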